10.4.6.3 Caching of Immediate Injection Site Observations by Nurses

To prevent unblinding of the physician investigators to the method of injection used, the immediate reactions observed by the unblinded injection nurses at the injection site (e.g., drop or flow of blood or wetness) for investigational doses 1 (Part 8, questions 1 to 8) and 2 (Part 11, questions 1 to 8) will be noted on separate colored pages (green 12enf and yellow 16enf, respectively) of the Case Report Form. For reasons of convenience, onto these removable colored pages will be moved other data items also completed by the nurses for dose 1 on page 11 (Part 7, questions 7 to 11) and for dose 2 on page 15 (Part 11, questions 7 to 11). For the injection, the nurses will separate and complete these pages and place them in a closed file in the injection room. After the investigational period of observation after dose 2, and after the physician investigator has entered all related assessments into the C.R.F. for a particular participant, these colored pages will be retrieved for insertion back into the rest of the C.R.F. and copied for forwarding to the CDC investigators for data entry and analysis.

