10.4.6 Blinding

The study will be observer-blinded. The study investigators, plus the study clinical staff who will assess and record adverse reactions, the laboratory personnel who will process and perform serological assays on the specimens, as well as the participant's parent(s) will all be unaware of the study group into which the participant is assigned. Only the

HIRRC/CDC Needle-free Intradermal	Page 73	File: 4785-ID-INF-Prot-Engl-2008Jun24.doc
Influenza Study - CDC-ISO-4785	of 138	2008-Jun-24

unblinded *injection nurse* and *holding assistant* will observe the method of injection. None of these unblinded staff will be involved in assessing or recording adverse events in the Case Report or other forms. Parents will be required to remain outside the injection room during the 1 to 2 minutes necessary to carry out the vaccination. The *allocation group randomization cards* (see 10.4.4.3) will be destroyed and discarded at the time when the device is filled for the associated participant. No written record of vaccination dose or route will be maintained in the study clinic.

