10.6.8 Vaccination Procedure

First, the injection nurses close the "injection cubicle" while the participant and parent remain outside. They open the **allocation group randomization envelope** (see section 10.4.4.3) for that child's dose (green for dose 1, yellow for dose 2, red for "insurance" dose 3). One injection nurse then shows the card to the other to confirm the dosage and method. Following the details described in section 10.4.2.3 above, the nurse duly prepares the syringe or jet injector cartridge, covers its tip to maintain cleanliness, and sets it down upon a clean surface and covers it.

The child is then brought into the "injection cubicle" and the parents are requested to remain outside. The **INF** vaccine is administered in the dose and route (ID or IM) specified by the randomization card into the anterolateral portion of the left thigh for children less than 12 months of age, or to the left deltoid muscle for children 12 months and older.

Immediately after the vaccination, the injection nurse will observe for several seconds the injection site for any wheal or bleb and any drops of blood or clear liquid, apply a band-aid, and duly note the information in the CRF, along with the time of injection. The *allocation card* is then destroyed and its pieces disposed into a paper shredder, and any remaining injection supplies or equipment removed from view.

The parent(s) and child are then reunited for holding and consoling (in the waiting area) during the subsequent minimum of 30 minutes of observation before reexamination of the injection site by the injection nurse (to avoid unblinding of the physican investigator from any temporary skin dimpling from the injector flange). During the post-vaccination waiting period, the parent/guardian will receive a final briefing and further training for aspects covered in section 10.6.4 above and reminded when to return next to the study center.

HIRRC/CDC Needle-free Intradermal	Page 94	File: 4785-ID-INF-Prot-Engl-2008Jun24.doc
Influenza Study - CDC-ISO-4785	of 138	2008-Jun-24

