10.6.11 Data Coding, Handling, and Analysis

As detailed in section 10.4.4 above, the blinding codes will be maintained in three secure locations by the independent party and other member(s) of the Data Safety Monitoring Board, as well as kept under seal by the HIRRC hospital director (in the BLUE envelopes, see 10.4.4.4). Codes will not be shared ("broken") with the study investigators (except as described in 10.4.4) until all clinical aspects of the study are completed and missing data obtained, and the serologic assays, performed blind, are completed and results shared.

Case Report Forms, Parent Diary, and other data recording sheets and forms from the study will be duplicated, with the originals kept in the HIRRC and complete copies furnished and maintained for analysis and preservation by the CDC. Data entry and analysis will be performed at CDC, with sharing of programming and data files with HIRRC (and with other parties at the discretion of the principal investigators once blinded laboratory assays are completed and results provided to CDC and HIRRC).

Once a CRF and its related forms are completed, verified, collected, and copied by the Dominican Principal Investigator, no additional information may be added to the originals. Any additions or corrections to the data of the CRF and related forms shall be made by means of the Data Clarification Form (DCF). This form (sections 11.4 and 13) shall be used to track inquiries to the clinical investigators from the sponsor (CDC) about entries in data fields of the Case Report Form, and/or to explain any subsequent changes in the data by the clinical investigators at HIRRC.

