It is very difficult for any vaccination study to document the amount of vaccine that actually enters the intended target tissue, whether skin (ID), muscle (IM), or fat (SC). Indeed, there is evidence that a substantial proportion of intended IM injections likely end up in the fat. Health workers have been found to underestimate the fat pad thickness in selecting needle length, or do not insert enough of it.^{Cockshott1982, Poland1997}

Proving the site of deposition or measuring the quantity of antigen reaching various tissue compartments would require contrast-imaging, biopsy, and similar expensive and invasive procedures. Regulatory agencies consider these unnecessary in most routine clinical trials because noninvasive measures and outcomes are available to document that the vaccine achieves its purpose. For ID injections, the presence of a wheal immediately after injection, and the absence of clear liquid drops on the skin, suggest that the dose went neither too deep nor too shallow. Both these variables will be collected in this study by observation immediately after vaccine doses 1 and 2 and noted on the Case Report Form.

In general for almost all vaccine trials, the immune response is empirical evidence of success. If antigen is placed into the wrong compartment in some participants, or partly escapes through the injection site, this would be an academic issue if participants are otherwise adequately protected from disease. If not, the immediate observations of the injection site may provide clues to any failure to effectively immunize, and provide a basis for further studies to elucidate the problem, if warranted.

HIRRC/CDC Needle-free Intradermal	Page 114	File: 4785-ID-INF-Prot-Engl-2008Jun24.doc
Influenza Study - CDC-ISO-4785	of 138	2008-Jun-24

12.6 Will the local side effects of intradermal injection be more painful for participants than needle-syringe?

The first studies of the Biojector with intradermal spacer were conducted by anesthesiologist professor Elemer Zsigmond at the University of Illinois (see 0), and suggested that ID injection was less painful than using a needle to administer lidocaine.^{Zsigmond1999a, Zsigmond1999b} Other clinical studies have demonstrated favorable safety and tolerability.

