trials for the investigational intradermal spacer (see section 10.4.3). To try to study intradermal delivery of any of these other jet injectors would require substantial additional resources and delay in conducting such prior studies in order ethically to justify the type of study intended here.

This study can be considered a *proof-of-principle* trial. If needle-free jet injection is demonstrated a safe and effective means of dose-sparing for influenza vaccination, it would serve to encourage other jet injector developers and manufacturers to pursue this route. The general concept of creating a gap between the orifice and the skin at the nozzle of a jet injector in order to weaken its stream to achieve intradermal injection is an old one (see section 9.6.3) and no longer under patent protection. Thus, other manufacturers would have freedom to adapt their own devices with gaps of appropriate length. This would help to produce a competitive marketplace for safer, simpler, and swifter intradermal delivery by jet injection.

12.9 What is the justification for giving the third "insurance" dose earlier than the routine annual revaccination? What are the risks, particularly for the control group which has already received the recommended two full doses?

It would be ideal if we could know immediately the results of the final blood draw on day 56 (8 weeks), so that we might avoid the inconvenience and expense of a third dose that day in those children who already have protective levels of antibody against influenza. But that is not possible.

Another option considered, but not chosen, would be to break the code of random allocation at the time of the final blood draw and vaccinate only those who had received the investigational low-dose regimens by ID or IM. These two groups might be at higher risk of not being protected than the control group which received the standard regimen for age and would not be indicated for revaccination until the next season. But it was decided that breaking the code so soon would severely compromise the study design. It may bias ascertainment for any delayed adverse events that may occur in the weeks and months after the active surveillance phase ends on day 56.

The primary reason for vaccinating on day 56 is to ensure that all participants are protected promptly against influenza, to which they might be exposed in the months ahead while waiting for antibody levels are being determined.

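### Nurse pages held back because they can reveal the injection method go to the CRF and the CDC investigators after each child's dose 2 period, while late safety work is still open

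*Protocol*

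**What the plan says.** Protocol 10.4.6.3 gives the reason for the separate pages: "To prevent unblinding of the physician investigators to the method of injection used, the immediate reactions observed by the unblinded injection nurses" are recorded on removable green and yellow sheets kept in a closed file in the injection room. The same paragraph sets the release point child by child: "After the investigational period of observation after dose 2, and after the physician investigator has entered all related assessments into the C.R.F". What happens at that point is also stated: "these colored pages will be retrieved for insertion back into the rest of the C.R.F. and copied for forwarding to the CDC investigators". The stated purpose of the copies is to enter and analyse the data.

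Other sections say who must stay blind, and for how long:

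- 10.4.6: "The study investigators, plus the study clinical staff who will assess and record adverse reactions", together with the laboratory and the parents, are to be unaware of the study group. Only the injection nurse and the holding assistant see the method.
- 10.6.11: codes are not shared with the investigators "until all clinical aspects of the study are completed and missing data obtained, and the serologic assays, performed blind, are completed" and the results shared. Section 10.4.6.1 instead places release at the end of the clinical and laboratory work of each phase.
- 12.9: breaking the code at the final blood draw was considered and rejected. One reason given is "It may bias ascertainment for any delayed adverse events that may occur in the weeks and months after" active surveillance ends on day 56.

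On content, 10.6.8 says "the injection nurse will observe for several seconds the injection site for any wheal or bleb" and for blood or clear liquid. Section 12.5 treats a wheal without liquid on the skin as a sign of proper intradermal delivery, and adds: "Both these variables will be collected in this study by observation immediately after vaccine doses 1 and 2 and noted on the Case Report Form".

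**The concern.** The protocol itself treats these observations as capable of revealing the injection method, yet it hands them to the people it is protecting before their work on that child is finished. It also goes to some trouble elsewhere to keep the method hidden at and after day 56. Controls receive a mock third injection, with an instruction not to tell parents or doctors (10.4.4.3), and the nurse rather than the physician does the early site check so that marks from the injector are not seen (10.6.8). Refiling the pages at about the same time undercuts both safeguards.

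At stake is the claim of observer blinding for late adverse events and for relatedness queries. For phase I, it is also at stake in the sponsor's freedom to decline phase II. An investigator who can tell which children were jet-injected may ask about, record or reconsider events differently in that arm.

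**Working it through.** There is no figure in the protocol to reproduce. The check sets the passages side by side, then looks at timing and at what the pages could reveal.

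**Who receives the pages, and who must be blind.** Under 10.4.6.3 the recipients are the site CRF, which the physician investigators use, and the CDC investigators. Section 10.4.6 requires the study investigators to be unaware of group and excepts only the two injection staff. Nothing in the protocol sends the pages to a separate unblinded data handler or holds them until code release.

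**Timing.**

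- Release: after the dose 2 observation period, nominally day 56. Table 6 allows that visit as late as day 98.
- Last safety inquiry: six months after day 56 (Table 5). At 30.44 days per month, 6 × 30.44 = 182.6 days, so about day 56 + 183 = 239.
- Serology: section 12.10 expects results to take several months or longer.

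On the nominal schedule the pages are therefore out about six months before that child's last adverse event inquiry. This precedes code release under either the per-phase wording of 10.4.6.1 or the end-of-study wording of 10.6.11.

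**What is still open at release.**

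- The inquiry on intervening adverse events at the bonus-dose visit (Table 5).
- External data clarification forms, which may concern the relation of an event to vaccination and are answered by the Dominican investigators (11.4).
- For phase I children, the phase II decision. Section 10.10 has the DSMB report without unblinded or group-specific information, and also lets the sponsor decline to proceed for any reason.

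**What is largely closed at release.**

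- That child's own assessments through the dose 2 period, because 10.4.6.3 makes their entry a condition of release.
- The HI assays, because the laboratory is blinded and nothing sends it CRF pages.

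**How much the pages reveal.** This cannot be computed, because the protocol gives no rates for the immediate observations. As an illustration only, suppose the wheal item is on these pages. Let w be the wheal rate after jet injection and f the rate after needle injection in each intramuscular arm. With 1:1:1 allocation, P(ID-JI-0.1 | wheal after one dose) = w / (w + 2f), against a prior of 1/3.

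- w = 0.60, f = 0.10: 0.60 / 0.80 = 0.75
- w = 0.90, f = 0.05: 0.90 / 1.00 = 0.90
- w = 0.95, f = 0.01: 0.95 / 0.97 = 0.98

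With no wheal at either dose, taking the doses as independent, each intramuscular arm has probability (1−f)² / [(1−w)² + 2(1−f)²]. This is 0.46 in the first case and 0.50 in the last, so the two needle arms cannot be told apart. All of these rates are assumptions; the point does not depend on them.

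**The case against.** The strongest reply is that no code is released. Sections 10.6.11 and 12.9 restrict the allocation code, and nurse observations are not the code. That stands. A reader might infer a direct breach of those two sections, but the text supports only a conflict with their purpose, together with a conflict with 10.4.6.

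The place of the wheal item is also inferred. Sections 10.4.6.3 and 10.1.3.2 name blood and wetness, while 10.6.8 and 12.5 say that a wheal is noted in the CRF without saying on which page. This stands too, and is why no size is claimed. It does not remove the point, since 10.4.6.3 itself says that the pages are withheld to prevent unblinding.

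Some wider readings are tempting but not supported:

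- That the stopping rules are broadly compromised. Serious events must be reported within 24 hours (10.5.2.2.5), so opinions on events in the day 0-56 window would normally be formed before that child's pages are refiled.
- That children still under observation are unblinded. Release is per participant, and their pages stay in the closed file.
- That the phase II criteria are applied with bias. The DSMB applies numerical rules using the true codes. What is exposed is the sponsor's separate discretion.

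Finally, holding the pages until code release would be partly circular, because 10.6.11 requires missing data to be obtained first. That is a fair objection to a simple hold, and the fix is ordered to meet it.

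**Conclusion.** The point holds in a limited form. Section 10.4.6.3 lets investigators who are meant to be blind infer jet versus needle for a child nominally from day 56, about six months before that child's last adverse event inquiry and while relatedness can still be queried. For phase I children this can also be before the sponsor decides on phase II. It defeats 10.4.6 and the purpose of 10.6.11 and 12.9 without literally releasing the code. It does not separate the two intramuscular arms, and it has little bearing on the serologic primary endpoint or on the day 0-28 reactions already entered. The extent of unblinding is unknown. The conclusion rests on the protocol's own statement of why the pages are withheld, and on reading the end of dose 2 observation as nominal day 56, since 10.4.6.3 sets no date. It should be corrected, but it does not threaten the main immunogenicity result.

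**What to change.** Replace the retrieval sentence in 10.4.6.3 with this sequence:

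1. The already unblinded injection nurses check the green and yellow pages for completeness when they fill them in.
2. The pages are then sealed and stay sealed until the 8-month inquiry, the other clinical data queries and the blinded assays are complete. The DSMB may have them earlier for its review under 10.10.
3. Only then are they refiled in the CRF, copied to the CDC investigators and entered, and any remaining queries on them resolved.
4. The code is then released under 10.6.11.

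The early check by the nurses, with entry of the pages before code release, lets the missing-data condition in 10.6.11 be met without circularity. The same edit should align 10.4.6.1 with 10.6.11 on whether release is per phase or at the end of the study. Withholding the pages does not impede the 10.10 criteria, which use none of the immediate blood, wetness or wheal observations. The cost is a short protocol change, plus later entry of these pages and later queries on them.

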10.4.7 Prior and Concomitant Therapy - Other Vaccinations

No other routine or investigational vaccines will be administered within 28 days before or after either of the study's investigational **INF** doses 1 or 2. As per the study exclusion criteria (see paragraph i. in section 10.3.2), otherwise eligible participants will not be recruited if they have received in the prior 28 days any routinely recommended vaccinations of the current Dominican Republic public immunization policy, or are due

HIRRC/CDC Needle-free Intradermal	Page 76	File: 4785-ID-INF-Prot-Engl-2008Jun24.doc
Influenza Study - CDC-ISO-4785	of 138	2008-Jun-24

to receive them in the following 56 days. The recommended Dominican immunization schedule indicates vaccines at 6 months (**POL**_{OPV}, **DTP**_w-**HBV**-**HIB**), 12 months (**MMR**), and 18 months (**POL**_{OPV}, **DTP**_w-**HBV**-**HIB**) of age. ^{SESPAS}

This restriction thus excludes infants "behind schedule" and needing to receive on the day of first interview protection against tuberculosis, polio, diphtheria, tetanus, pertussis, hepatitis B, *Haemophilus influenzae* type b, measles, mumps, or rubella. It also creates three gaps in the intended ≥ 6 -to- <24 months age range of recruited participants for this study. The first gap would be ages <7 months (unless the participant received his or her third **POL**_{OPV} and **DTP**_w-**HBV**-**HIB** doses at ≤ 5 months); the second gap from >10 -to- <13 months; and the third gap from >16 -to- <19 months.

If, in the opinion of the Dominican investigators, a child may benefit by immediately receiving another vaccine during the 28-day-period after either of the study's influenza vaccine doses (e.g., because of exposure to meningitis or another vaccine-preventable disease), such other vaccines should be administered by the appropriate authority and duly noted on the Case Report Form, part 20.

10.4.8 Treatment Compliance and Participant Incentives

Adherence of study participants to the vaccination and visit schedule will be supervised by the study nurses and senior clinical staff. A total of 8 visits are planned, on days 0, 2, 7, 28 (4 weeks), 30, 35, 56 (8 weeks), and 8 months (see **Table 5** in section 10.6.1 for details).

Parents will be encouraged to return with their infant, diary form, and related items for scheduled clinic visits through the provision of modest incentives, which may include:

- round trip taxi fares from and to home
- voucher for lunch or snack in the hospital snack bar
- folder and pencils for storing and marking take-home materials (diary form, measuring tape and template, adhesive thermometers)

For those children who do not return to the clinic as scheduled, study health workers will collect the information by telephone, reschedule the visit, and/or make home visits on the days following the missed scheduled visit.

10.5 Efficacy and Safety Variables

10.5.1 Efficacy

10.5.1.1 Immunogenicity

In this trial, the surrogate for measuring actual field efficacy (protection from actual disease through natural exposure to wild virus) will be the immune responses generally considered predictive of such protection.

10.5.1.2 Primary Efficacy Variable

Seroconversion (SC) is the primary efficacy variable. It is defined as the development of an inverse hemagglutination inhibition (HI) titer of \geq 40 on *followup* serum collected one month after the second vaccine dose among initially-seronegative participants (undetectable inverse titer of <8 on *baseline* day 0); OR, for participants with a detectable *baseline* titer, the development of a *followup* HI titer which rises \geq 4-fold. (Usually analyzed as a proportion among participants.)

10.5.1.3 Secondary Efficacy Variables

Secondary efficacy variables are:

Seroprotection (SP), defined as the development of an inverse HI titer of \geq 40 on *followup* serum collected one month after the second vaccine dose, regardless of evidence of immunity at *baseline*. (Usually analyzed as a proportion among participants.)

Mean geometric increase, defined as the ratio of the geometric mean titers (GMT) of all participants on *followup* HI assay divided by the GMT of HI assay on the same participants at *baseline* (excludes participants with baseline titers lost to followup). (For example, a mean baseline inverse GMT of 18 and followup of 81 would have a mean geometric increase of 4.5.)

Dose 1 seroconversion, defined according to the seroconversion criteria above one month after only the first dose of influenza vaccine, before receiving dose 2.

Dose 1 seroprotection, defined according to the seroprotection criteria above one month after only the first dose of influenza vaccine, before receiving dose 2.

Dose 1 mean geometric increase, defined according to the mean geometric increase calculation above after only the first dose of influenza vaccine, before receiving dose 2.

